## 8. BIOLOGICAL SAMPLING PROCEDURES

### 8.1 Volume of blood

The patients usually stay in the intensive care unit for 2-4 days depending on the postoperative course. Each day during the stay at the ICU, 10-15 mL blood for routine laboratory screen will be drawn. The amount of blood may increase to 25-30 mL in case of complicated postoperative conditions (disease/operation/post operative course).

In the present study extra blood will be drawn for the analysis of study-specific biomarkers e.g. inflammatory markers and the complement system, NGAL and markers of neuronal injuries.

The total volume of extra blood that will be drawn from each subject in this study is shown in Table 5.

**Table 5** *Volume of blood to be drawn from each subject*

	Time point	mL blood
T0	Prior to CPB	2 mL
T1	At the end of CPB	2 mL
T2	2 hours after termination of CPB	2 mL
T3	6 hours after termination of CPB	2 mL
T4	24 hours after termination of CPB	2 mL
At day 5 or at discharge from hospital		2 mL
Total		12 mL

The total amount of blood taken extra from the included patients will be 10 mL in the operation day and the first postoperative day. The following table shows the proportion of the extra blood taken from an included patient compared with that amount of the blood needed for normal routine clinical use. The patient in this example has a weight of 3.5 kg and a blood volume of 90 mL/kg (total blood volume  $3.5 \times 90 = 315$  mL). It should be noted that the majority of pediatric cardiac surgery patients receive either blood products or blood (or both), and the length of stay may be considerably longer. In addition to blood drawn according to table 1, at day 5 or at the discharge from hospital 2 mL blood will be drawn for among others the analysis of Levosimendan metabolites (pharmacokinetics).

**Table 6** *Blood taken for lab screen and for study-specific analyses*

Days in PICU	Routine blood samples in uncomplicated cases mL (% of total blood vol.)	Routine blood samples in complicated cases mL (% of total blood vol.)	Blood taken for this study mL (% of total blood vol.)
Day 1 (operation day)	15 (4.8 %)	30 (9.5%)	10 (3.2%)
Day 2	15 (4.8 %)	30 (9.5%)	-
Day 3	15 (4.8 %)	30 (9.5%)	-
Total after 3 PICU days	45 (14.4 %)	90 (28.5 %)	10 (3.2%)

## **8.2 Handling, storage and destruction of biological samples**

The samples for routine analysis will be used up or disposed after analyses and are not applicable for Biobank.

The blood samples will be analysed after finalized study. A minor amount of the biological samples from each patient will be stored in Biobank at the hospital for a maximum of 15 years for future research. The results from future analysis will not be reported in the Clinical Study Report but separately in a Clinical Study Report Amendment and/or Scientific Report or Scientific Publication.

A full chain of custody is maintained for all samples throughout their lifecycle.

The principal investigator keeps full tractability of collected biological samples from the subjects while in storage at the centre.

The sample receiver keeps full tractability of the samples while in storage and during use until used or disposed.

## **9. STUDY AND DATA MANAGEMENT**

### **9.1 Audits and inspections**

A regulatory authority or the Ethics Committee may perform audits or inspections at the centre, including source data verification. The purpose of an audit or inspection is to systematically and independently examine all study-related activities and documents, to determine whether these activities were conducted, and data were recorded, analysed, and accurately reported according to the protocol, Good Clinical Practice (GCP), guidelines of the International Conference on Harmonisation (ICH), and any applicable regulatory requirements.

## **9.2 Recording of data**

Paper case record forms (CRF), will be used to record all data. Data entry, editing and analyses will be done by the responsible investigators and study nurse(s). The investigators will ensure that all data collected in the study will be provided. He/she ensures the accuracy, completeness, legibility and timeliness of the data recorded in the appropriate sections of the CRF and according to any instructions provided.

Clean File/database lock must be documented. The reason for any excluded data or protocol deviations will be described in the study report. Any changes in the database after Clean File/database lock must be documented.

Data will thereafter be entered into an Excel datasheet and analysed with S.P.S.S.19 statistical software.

CRF documentation and other source data will be retained for at least 10 years after finalization of the clinical study.

### **9.2.1 Source data**

All patient source data such as analysis results from the hospital laboratories and other measurements made e.g. ECG readings will be stored at the hospital according to routines.

The CRFs serves as the source for demographic data, medical history and physical examination and measurements as well as blood analysis.

## **9.3 Training of study site personnel**

The principal investigator will ensure that appropriate training relevant to the study is given to all of these staff, and that any new information relevant to the performance of this study is forwarded to the staff involved.

The principal investigator will maintain a record of all individuals involved in the study (medical, nursing and other staff).

## **9.4 Monitoring of the study**

An independent study nurse not directly involved in the study will be appointed for monitoring the study. The monitor will be appropriately trained and informed about the

nature of the study, patient written information, GCP and applicable regulatory requirements. Monitor's qualifications will be documented.

The monitor will verify informed consents of participating subjects, confirm that facilities remain acceptable, that the investigational team is adhering to the protocol that data are being accurately recorded in the Case Report Forms (CRF) and that therapy accountability is being carried out. The monitor will also ensure source data verification (comparison of the data in the CRF with the hospital/practice and other records at the investigational site).

## **10. STATISTICAL METHODS AND SAMPLE SIZE**

### **10.1 Sample size calculation**

The number of patients needed for the study is based on a 20% reduction in creatinine in the Levosimendan group compared with the Milrinone group in the day after stopping the infusion of Levosimendan/Milrinone (second postoperative day). The power of study is set on 80 %.

The study will contain two groups; Levosimendan (n=35) and Milrinone n=35). Patients in the Levosimendan group will receive Levosimendan as inotrope agent and patients in the Milrinone group will receive Milrinone as inotrope agent. Patients will randomly be assigned to either group. The caregivers (physicians, nurses and nurse-assistants) will be blinded for the study. The same infusion rate and total volume of Levosimendan and Milrinone will be applied to both groups.

### **10.2 Statistical analysis**

Analysis of data will be performed by a professional statistician. T-test for independent groups will be used for primary outcome. Descriptive statistics will be applied on the secondary outcomes including 30-days mortality, length of hospital stay and kidney function 5 days after start of infusion of Milrinone/Levosimendan. Additionally, clinical data (fluid balance, length of surgery, length of CPB, length of mechanical ventilation postoperatively, length of vasoactive therapy, number of vasoactive medications, total amount of infused vasoactive drugs, hemodynamic parameters) will be registered and analyzed. Univariate analyses will be used where needed. Multivariable regression analysis will be used to identify association between the occurrences of AKI (based on creatinine results) and the measured clinical variables.

Clinical Study Protocol  
Study Code: MiLe-1  
Drug Substance: Levosimendan  
EudraCT No: 013-003105-25  
Date

Other statistical methods might be used in an exploratory fashion but no formal inference will be made.

Safety and tolerability data will be summarized descriptively by treatment and presented in tabular and/or graphical form. All adverse event data will be listed individually and summarized using MedDRA terminology.

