1 STUDY DETAILS

1.1 Study Objectives

The aim of the study is to assess the ability of Levosimendan to reduce the postoperative acute kidney injury in pediatric patients undergoing surgery for congenital heart disease (CHDs).

The primary objective of this study is to investigate the preventive effect of Levosimendan on postoperative acute kidney injury in pediatric patients undergoing surgery for their CHDs. Creatinine at the second postoperative day will be the primary endpoint.

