5.5.2 Secondary Efficacy Analyses

Complementary analyses of the primary analysis will be made up to 72 hours and also one analysis up to 96 hours in the same fashion as the primary analysis.

Secondary variables will be presented at each timepoint and changes from baseline (screening, pre-op) will be calculated where applicable. T-test for independent groups will be used for secondary continuous outcomes if the data not is clearly non-normal distributed. If baseline values differs between groups adjustment for baseline values will be made using a covariance analysis will be made. If the outcome is clearly non normal distributed Fishers non parametric permutation test will be used instead of t-test.

Categorical (no/yes) variables will be analysed between groups by using Fisher exact test.

Univariable and multivariable logistic regression analysis will be used to identify association between the occurrences of AKI (based on creatinine results) and the measured clinical variables.

STATISTISKA KONSULTGRUPPEN		Statistical Analysis Plan
Protocol: The prophylactic effect of Levosimendan in reducing acute kidney injury postoperatively in pediatric patients undergoing corrective heart surgery	Protocol No: MiLe-1	Version: 1.0
		Page 16 of 17

5.5.3 *Exploratory Efficacy Analyses*

Selected correlation analyses will be performed between secondary variables/outcomes.

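### Day-2 creatinine is adjusted for its pre-operative value only if an undefined baseline difference appears, so the comparison the trial was sized on forgoes most of the power that routine ANCOVA would give

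*Protocol*

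**What the plan says.** **Sizing.** Protocol 10.1 derives the number of patients from one comparison. It is "based on a 20% reduction in creatinine in the Levosimendan group compared with the Milrinone group in the day after stopping" the infusion, which the section identifies as the second postoperative day. Power is 80%, with 35 infants per arm. SAP 1.4 repeats this.

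**Test in the protocol.** Section 10.2: "T-test for independent groups will be used for primary outcome". No covariate is named.

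**Status in the SAP.** Section 1.1 states "Creatinine at the second postoperative day will be the primary endpoint". Sections 4.4.1 and 5.5.1 nevertheless define the primary outcome as binary AKI within 48 hours, analysed by logistic regression, and 4.4.3 lists creatinine and corrected creatinine as secondary. Section 7, which should record changes from the protocol, holds only a template instruction.

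**Test in the SAP.** Section 5.5.2: "T-test for independent groups will be used for secondary continuous outcomes if the data not is clearly non-normal distributed". It then provides for a covariance analysis when baseline values differ between the groups, but gives no criterion for differing. Clearly non-normal data go to a permutation test. Changes from baseline are to be calculated where applicable.

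**Baseline data.** SAP 4.1.3 lists creatinine, eGFR and cystatin C in the pre-operative samples, and SAP 4.4.2 has a T0 time point just before bypass for NGAL. Study drug starts during bypass (protocol 6.1), so these values precede it.

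**The concern.** A pre-operative measurement of the same quantity is planned, and the default analysis leaves it out. Any part of the day-2 variation that the pre-operative value would explain stays in the error term and widens the interval for the comparison behind the sample size.

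The conditional rule uses the wrong signal. In a randomised trial a baseline difference between arms is chance. What a covariate gains in precision depends on how strongly it predicts the outcome, and that gain is available whether or not the arms happen to differ at baseline. Because the trigger is undefined, the model is also chosen after the data are seen, by a judgement that two analysts could make differently.

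**Working it through.** **Inputs from the documents.** 35 per arm, 20% relative reduction, 80% power (protocol 10.1); two-sided alpha 0.05 (SAP 5.1; protocol 10.1 states no alpha).

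**Inputs not in the documents.** The control mean, the SD or coefficient of variation (CV) of day-2 creatinine, and the correlation rho between pre-operative and day-2 creatinine. Rho is assumed, mainly over 0.3 to 0.7.

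**Step 1: the plan's own figure.** Without an SD, n = 35 per arm cannot be reproduced. It can be solved backwards for the CV that makes it true:

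CV = 0.20 / [(1.960 + 0.842) × √(2/35)] = 0.20 / 0.670 = 0.299.

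The noncentral t with 68 df gives 0.294, a standardised difference d = 0.20 / 0.294 = 0.68 (0.679 unrounded). The next steps hold the SD at this value, so that the t-test has exactly its nominal 80%.

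**Step 2: ANCOVA in every case.** The residual SD is SD × √(1 − rho²), so the effective standardised difference is d / √(1 − rho²), with 67 df. The equivalent sample size is 35 × (1 − rho²), rounded up.

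| rho | Power | Gain over 80% | Infants per arm for 80% |
|---|---|---|---|
| 0.2 | 81.6% | 1.6 points | 34 |
| 0.3 | 83.6% | 3.6 points | 32 |
| 0.5 | 89.9% | 9.9 points | 27 |
| 0.7 | 97.5% | 17.5 points | 18 |

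At rho 0.5, 35 × 0.75 = 26.25, hence 27.

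**Step 3: the SAP's conditional rule.** The rule was read as ANCOVA if a t-test on baseline gives p<0.05, otherwise the unadjusted t-test. There were 20,000 simulated trials per setting, with bivariate normal data and 35 per arm.

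| rho | Power: t-test | Power: conditional rule | Power: always ANCOVA | Type I error: conditional rule |
|---|---|---|---|---|
| 0.3 | 80.1% | 80.3% | 83.1% | 4.9% |
| 0.5 | 80.1% | 80.9% | 89.6% | 4.5% |
| 0.7 | 79.9% | 81.8% | 97.5% | 3.8% |

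Simulation standard errors are about 0.28 points for power, √(0.8 × 0.2 / 20,000), and 0.15 points for type I error, √(0.05 × 0.95 / 20,000). Always-ANCOVA kept its type I error at 5.0% to 5.2%.

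The reason is simple. On this reading randomisation triggers the adjustment in about 1 trial in 20, so the other 19 are analysed by the t-test. The trials that are switched are those in which chance imbalance would most often have produced a false positive, which is why the type I error drops below 5%.

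**Step 4: sensitivity to the SD.** If the CV is really 0.40, the t-test has 55.2% power, and always-ANCOVA has 59.2%, 67.6% and 83.4% at rho 0.3, 0.5 and 0.7 (normal approximation).

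**Step 5: change from baseline.** With equal SDs at both times the effective difference is d / √(2(1 − rho)). Power is 65.8% at rho 0.3, 72.5% at 0.4, 80.0% at 0.5 and 87.9% at 0.6. A t-test on change is therefore worse than the raw comparison below rho 0.5, and below ANCOVA at each of these values (ANCOVA: 83.6%, 86.3%, 89.9%, 93.8%).

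**The case against.** **The plan already contains ANCOVA.** A reader who sees only protocol 10.2 might infer that creatinine is never adjusted. SAP 5.5.2 does not support that, because covariance analysis is foreseen when baselines differ. This stands. The criticism is of the trigger, which under the p<0.05 reading gives back at most about 2 points of power. A looser trigger would be used more often and recover more, but only an unconditional rule recovers all of it.

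**Creatinine is no longer the primary analysis.** A reader might infer from the sample-size link that the trial's primary test is affected. Under SAP 4.4.1 and 5.5.1 it is not, since that test is the AKI logistic regression. This also stands. Day-2 creatinine is still the only outcome the sample size was derived for, and SAP 1.1 still calls it primary. The conflict between those sections is a separate matter.

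**Not every infant will have a baseline value.** SAP 5.3 foresees missing baseline creatinine as a major deviation, and the ITT definition (SAP 3.1.1) requires only a follow-up creatinine. A complete-case ANCOVA would drop such infants from ITT. This stands, and the remedy has to deal with it.

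**The gain may be small.** Excluding any kidney dysfunction (protocol 4.2) may narrow the baseline range and lower rho. At rho 0.1 ANCOVA power is 80.4%. The size therefore cannot be fixed from the documents; only the direction and the negligible cost can.

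**Change scores.** SAP 5.5.2 calculates changes but does not say that creatinine is tested on them. Step 5 is a caution and does not describe a planned test.

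**Conclusion.** The point holds as an efficiency and pre-specification weakness in a comparison that the SAP treats as secondary. An unadjusted t-test in a randomised trial is valid, so nothing here implies bias. A reader might also infer a fixed loss of about 10 points, but that is only the rho 0.5 case.

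At the SD implied by the plan's own sample size, always adjusting adds about 4 to 18 points of power for rho 0.3 to 0.7, and about 1.6 points at rho 0.2. The conditional rule adds about 0.2 to 2 points over rho 0.3 to 0.7, with type I error between 4.9% and 3.8%. These figures assume the back-solved SD, approximately normal data, a linear baseline relation and the p<0.05 reading of the trigger. Since no SD is stated, the nominal 80% is itself not assured, which makes a free gain in precision more worth having. The change should be made.

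**What to change.** In SAP 5.5.2, and in protocol 10.2 for consistency:

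- Delete the condition that adjustment depends on baseline values differing between groups.
- Pre-specify ANCOVA of day-2 creatinine on treatment and pre-operative creatinine in all cases. Use the log scale if the data are skewed, and report the adjusted difference (a ratio on the log scale) with its 95% CI. State which creatinine version in SAP 4.4.3 is meant.
- Keep infants with a missing baseline in the ITT analysis by a simple pre-specified rule, for example imputing the baseline covariate with its mean over both arms.
- Use the same form for cystatin C, eGFR and NGAL (with T0 as covariate).
- Report changes from baseline descriptively only.

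Record the change in SAP section 7. The stratification factors in protocol 4.3.1, diagnosis and age, could enter the same model; the figures above do not include them.

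The cost is one degree of freedom for the covariate and wording changes in the SAP, plus a protocol amendment if 10.2 is aligned. No extra infants, samples or visits are needed.

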## **11. STUDY TIMETABLE AND END OF STUDY**

The study will be terminated when the follow-up of the last patient included is completed. The follow-up period for each patient included is 4 days after termination of Levosimendan/Milrinone infusion.

First Subject in: June 2014. Last Subject Last Visit: June 2016

Final Study Report: within 12 months from end of study.

## Appendix B - The preparation of the study drugs and the doses

---

### 13. PREPARATION OF THE STUDY DRUGS

#### 13.1 Logistics

Logistically, it is not possible to use the hospital pharmacy for preparation dilution of the study medications. The hospital pharmacy does not offer such a service. Hence, we should do this by ourselves, using "Drug Cards" currently used in our department; Department of Pediatric Anesthesia and Intensive Care. The Drug Cards has been produced as a result of cooperation between the hospital pharmacy and the clinicians. In our department, the nurses prepare all the drugs we currently use. The nurses, who are either specialist in anesthesia or specialist in intensive care do this according to our strictly regulated routines.

#### 13.2 Levosimendan and Milrinone preparations

Levosimendan and Milrinone, prepared according to the Drug Cards, have different final concentrations; Levosimendan 0.05 mg/mL and Milrinone 0.2 mg/mL. Despite this, Levosimendan and Milrinone have fairly similar infusion rates to deliver a normal dose of the drugs to the patients; Levosimendan 0.12 mL / kg / hr and Milrinone 0.15 mL / kg / hr. These infusion rates supply the patient with 0.1 µg / kg / min of Levosimendan and 0.5 µg / kg / min of Milrinone

#### 13.3 Infusion rate for a normal dose

Because the study is blinded, we must have the same infusion rate in each included patient. If we have an infusion rate of 0.12 mL / kg / hr, then we deliver 0.1 µg / kg / min of Levosimendan (normal dose) and 0.4 µg / kg / min of Milrinone. The normal dose of Milrinone is 0.3 - 1.0 µg / kg / min. In the clinic, we begin normally infuse Milrinone at a rate of 0.15 mL / kg / hr which corresponds a dose 0.5 µg / kg / min. **Hence, the infusion rate of the drugs in this study is 0.12 mL / kg / hr.** If the patient needs more inotropic support there are two options; delivering a bolus doses (or half-bolus dose) or doubling the dose continuously.

### 13.4 Bolus dose / half-bolus dose

For administration of bolus doses, we should use the same principle that is the volume of the bolus dose should be constant and this volume should deliver the actual bolus dose for both drugs. The bolus dose for Levosimendan is 12  $\mu\text{g}/\text{kg}$  given in ten minutes. An infusion rate of 1.44 ml / kg / hr in ten minutes (a maximum volume 0.24 ml / kg) delivers this volume dose. In case of Milrinone, 1.44 ml / kg / hr in ten minutes (a maximum volume 0.24 ml / kg) delivers 48  $\mu\text{g}$  / kg of the drug. The standard loading dose of Milrinone is 50  $\mu\text{g}$  / kg. **Hence, the bolus dose in this study is administered as 1.44 ml / kg / hr in ten minutes (a maximum volume 0.24 ml / kg).** To deliver a half-bolus dose we infuse 0.72 mL / kg / hr for 10 minutes (a maximum volume 0.12 ml / kg).

### 13.5 Doubling the dose continuously

If we double the infusion rate to 0.24 ml / kg / hr, this delivers 0.2  $\mu\text{g}$  / kg / min of Levosimendan (maximum dose of Levosimendan) and 0.8  $\mu\text{g}$  / kg / min of Milrinone. Maximum dose of Milrinone is 1.0  $\mu\text{g}$  / kg / min.

### 13.6 The calculations

#### 13.6.1 Infusion rate and the dose delivered

What dose do we deliver to the patient with a infusion rate of 0.12 mL/kg/hr?

Infusion rate	Delivers
0.15 mL/kg/hr	0.5 $\mu\text{g}/\text{kg}/\text{min}$
0.12 mL/kg/hr	$X = 0.12 \times 0.5 / 0.15 = 0.4 \mu\text{g}/\text{kg}/\text{min}$

#### 13.6.2 Bolus dose

##### 13.6.2.1 Levosimendan

Is it correct that bolus infusion rate of 1.44 mL/kg/hr in ten minutes delivers 12  $\mu\text{g}/\text{kg}$  of Levosimendan? The concentration of Levosimendan is 0.05 mg/mL.

mL	minutes	

Clinical Study Protocol  
Study Code: MiLe-1  
Drug Substance: Levosimendan  
EudraCT No: 013-003105-25  
Date

1.44	60	
x	10	$X = 1.44 \times 10 / 60 = 0.24 \text{ mL}$

This means that in 10 minutes we deliver 0.24 mL of Levosimendan. How much active drug is in this volume?

mL	mg	
1	0.05	
0.24	X	$X = 0.05 \times 0.24 / 1 = 0.012 \text{ mg} = 12 \mu\text{g}$

Hence, it is correct, 1.44 mL/kg/hr in ten minutes delivers 12  $\mu\text{g}/\text{kg}$  of Levosimendan.

### 13.6.2.2 Milrinone

How much active drug is delivered with the bolus infusion rate of 1.44 mL/kg/hr in ten minutes? The concentration of Milrinone is 0.2 mg/mL.

mL	min	
1.44	60	
X	10	$X = 1.44 \times 10 / 60 = 0.24 \text{ mL}$

mL	mg	
1	0.2	
0.24	X	$X = 0.2 \times 0.24 / 1 = 0.048 \text{ mg} = 48 \mu\text{g}$

Clinical Study Protocol

Study Code: MiLe-1

Drug Substance: Levosimendan

EudraCT No: 013-003105-25

Date

